4.0 TREATMENT PLAN

4.1 Overview

All subjects will be treated in cycles lasting 21 days (3 weeks). The drugs being used in this study include pembrolizumab and guadecitabine. Guadecitabine 30mg/m² will be administered as a subcutaneous injection on Days 1-4 of every 21 day cycle. Pembrolizumab 200 mg will be administered as a 30 minute IV infusion on Day 5 of every 21 day cycle. ***Patients must begin therapy within (+) 14 days of registration.***

For patients on combination therapy, treatment should be initiated on Day 1 of each cycle. NOTE: For patients receiving the combination of guadecitabine and pembrolizumab, guadecitabine dosing on Day 1 of each cycle should always begin on a Monday in order for the patient to receive pembrolizumab on Friday (Day 5). In the event of holidays or scheduling difficulties for administrative reasons, Day 1 of each cycle may be delayed up to +28 days. All treatments will be administered on an outpatient basis. Treatment will continue until disease progression, unacceptable toxicity, patient withdrawal, or death. NOTE: please see section 4.4.1 for conditions under which patients may be permitted to continue on single agent pembrolizumab only. One dose of guadecitabine may be skipped during a cycle due to scheduling constraints with holidays (e.g. if Memorial Day is on a weekday, the patient may skip that dose of guadecitabine). The decision to skip a dose of guadecitabine vs dose delay will be at the discretion of the treating physician.

Please refer to Section 5.2 (table) for treatment details regarding patients on Pembrolizumab monotherapy.

To exclude prohibitive toxicity, a safety run-in cohort of the initial 6 patients will be done. All subjects in the run-in cohort will be observed for at least 2 weeks after completion of cycle 1 for dose limiting toxicity (DLT) (Refer section 4.3)

4.2 Treatment Administration

Agent ²	Dose	Route	Schedule ²	Cycle Length
Pembrolizumab	200 mg	IV infusion	Day 5 of each 3 week cycle (Q3W)	21days (3 weeks)
.Guadecitabine ^{1,2}	30mg/m ²	SQ injection	Days 1-4 of each cycle (QD for 4 days)	

¹ The starting dose for guadecitabine is 30 mg/m²; in the event that dose reduction is necessary (see 4.4.1), dose level -1 will be 24 mg/m². There are no further dose reductions.

Note: Guadecitabine priming can be discontinued and the patient can continue on pembrolizumab monotherapy, after 6 months (8 cycles) at the discretion of the treating physician, if the patient has stable disease or response. If this is done, the previously scheduled pembrolizumab treatment on Day 5 will become Day 1(+/-2 days. Please refer to Section 5.2 (table) for treatment details regarding patients on Pembrolizumab monotherapy.

For patients who discontinued guadecitabine for reasons other than toxicity (i.e. disease stability of response > 6 months) and progress on pembrolizumab alone, a re-trial of guadecitabine in combination with pembrolizumab is possible, at the discretion of the treating physician, if the patient is clinically stable.

² After completion of the safety run in, starting on Day 5 of each cycle, growth factor support filgrastim or peg filgrastim can be administered 24 hours after completion of

NU Study Number: NU 16G03

Merck Study Number: 3475-244

guadecitabine administration, at the discretion of the treating physician.

4.2.1 Pembrolizumab

Pembrolizumab 200 mg will be administered as a 30-minute intravenous (IV) infusion every 3 weeks. Every effort should be made to target infusion timing to be as close to 30 minutes as possible. However, given the variability of infusion pumps, a window of -5 minutes and +10 minutes is permitted (i.e., infusion duration is 30 minutes: -5 min/+10 min).

Pembrolizumab does not require any pre-medications unless clinically indicated for an infusion reaction. Local institutional practices should be followed in case of an infusion reaction.

Please refer section 8.1 and to the separate Pharmacy Manual for specific instructions regarding the preparation of the pembrolizumab infusion fluid and administration of infusion solution.

4.2.2 Guadecitabine

Guadecitabine 30mg/m² will be administered as a subcutaneous injection on Days 1-4 of every 3-week cycle. Patients are required to come to the clinic for administration of the drug. Pre-medications are not required.

Baseline weight will be used throughout. Dose will not change with weight changes.

Note: Guadecitabine priming can be discontinued and the patient can continue on pembrolizumab monotherapy after 6 months (8 cycles), at the discretion of the treating physician, if the patient has stable disease or response. For patients who discontinued guadecitabine for reasons other than toxicity (i.e. disease stability of response > 6 months) and progress on pembrolizumab alone, a re-trial of guadecitabine in combination with pembrolizumab is possible, at the discretion of the treating physician, if the patient is clinically stable.

4.3 Safety Run-in Cohort

Drug interaction and increased toxicity is not anticipated; however, there is no clinical experience with the combination of guadecitabine and pembrolizumab. To exclude prohibitive toxicity, up to 6 subjects will be treated with combined therapy as outlined in Table 2. If a subject goes off study before completing the DLT observation period of safety run-in for reasons other than DLT, then that subject should be replaced.

Accrual will be suspended after the initial 6 subjects have been enrolled. All subjects in the run-in cohort will be observed for at least 2 weeks after completion of cycle 1 for dose limiting toxicity (DLT) as defined in Table 3 below. An event must be at least "possibly related" to either Pembrolizumab or Guadecitabine to be considered as DLT

Table 3: Definition of Dose Limiting Toxicities (DLT)

Toxicity Category	Criteria Defining a DLT
Hematological*	Grade 4 treatment-related neutropenia lasting for \geq 7 days
	Grade 4 treatment-related febrile neutropenia
	Grade 3 treatment-related thrombocytopenia lasting \geq 7 days associated with bleeding or Grade 4 treatment-related thrombocytopenia lasting \geq 4 days
Non-hematological	Grade \geq 3 treatment-related toxicity despite the use of adequate/maximal medical interventions and/or prophylaxis as dictated by local institutional clinical practices or the judgment of the Investigator.
Any toxicity that is possibly, probably or definitely related to study drug that results in a >14 day delay in cycle 2 Day 1 dosing will also be considered a DLT.	

*No growth factor is allowed

If 0 or 1 out of 6 subjects in the safety cohort experiences a DLT, accrual to the rest of the study will commence. If 2 or more of 6 subjects in the safety lead in cohort experience a DLT, the study will be suspended and an amendment to explore lower doses or a longer treatment interval (28 day cycle) will be considered.

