4.4.1 Dose modifications for Guadecitabine

Guadecitabine-related AEs will be managed with dose reductions and/or skipped doses. Guadecitabine dosing should be held for \geq grade 3 neutropenia, \geq grade 3 thrombocytopenia or other \geq grade 3 guadecitabine-related non-hematologic toxicities until toxicity has resolved to \leq Grade 1 or baseline levels (NOTE: pembrolizumab dosing may continue for that cycle if the toxicity is documented to be related only to guadecitabine). Treatment with guadecitabine may then be resumed for the next cycle at dose level -1 (which is 24 mg/m² – see Section 4.2). Missed doses will not be made up. Exceptions for the dose reductions would include neutropenia and anemia which could be managed by growth factors and transfusion, and in that case dosing may be resumed at the same dose level. After completion of the safety run in, starting on Day 5 of each cycle, growth factor support filgrastim or peg filgrastim can be administered 24 hours after completion of guadecitabine administration, at the discretion of the treating physician.

NU Study Number: NU 16G03
Merck Study Number: 3475-244

If the subject still has drug-related clinically significant toxicity that has not resolved to ≤ Grade 1 or baseline by the time of the next cycle, dosing for that cycle may be delayed 1 week (7 days). Dosing may restart at dose level -1 (24 mg/m²) once the toxicity has resolved to ≤ Grade 1 or baseline. If toxicity is still not resolved after a delay of 1 week, guadecitabine will be discontinued. If the patient has already completed 2 cycles of combination therapy at this point, the patient may be a candidate for continuing on single-agent pembrolizumab (see below).

If grade 3-4 toxicity reoccurs after treatment has been restarted at dose level -1 (24mg/m²), and the patient has received at least 2 cycles of guadecitabine priming, then guadecitabine can be discontinued permanently and pembrolizumab can be continued as a single agent on the same dose schedule.

Rationale for continuing single-agent pembrolizumab:

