There is presumptive scientific rationale that treatment with a hypomethylating agent will cause re-expression of tumor antigens within the first 2 cycles, and thus epigenetic priming, which enhances the effects of immunotherapy. Therefore, it is reasonable to continue treatment with single agent pembrolizumab after epigenetic priming has been induced. If a patient cannot complete at least 2 cycles of guadecitabine and pembrolizumab combination, then she would be discontinued from the study.

Please note: Guadecitabine priming can be discontinued and the patient can continue on pembrolizumab monotherapy after 6 months (8 cycles), at the discretion of the treating physician, if the patient has stable disease or response. For patients who discontinued guadecitabine for reasons other than toxicity (i.e. disease stability of response > 6 months) and progress on pembrolizumab alone, a re-trial of guadecitabine in combination with pembrolizumab is possible, at the discretion of the treating physician, if the patient is clinically stable.

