4.8 Duration of Therapy

Patients may continue to receive cycles of treatment until any of the following occur:

- Disease progression as defined by RECISTv 1.1
- Delay of more than 28 days due to treatment related toxicity (toxicities possibly, probably or definitely related to the drug) will result in discontinuation of study drugs.

(Note: It does not include toxicities clearly not related to the drug such as disease progression, environmental, unrelated trauma, etc.)

- Development of an inter-current illness that prevents further administration of treatment.
- Unacceptable adverse event(s).
- Patient decides to withdraw from either study treatment or the study as a whole.
- The treating investigator determines that the patient should be taken off treatment for any reason (i.e. changes in condition, inability to comply with study treatment or procedures).
- Discontinuation of treatment may be considered for subjects who have attained a confirmed CR that have been treated for at least 24 weeks with pembrolizumab and had at least two treatments with pembrolizumab beyond the date when the initial CR was declared.

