4.11 Patient Replacement

If a patient is enrolled in the study but comes off study prior to the first dose of treatment, the patient may be replaced.

If a subject in the safety run-in portion of the trial goes off treatment before completing the DLT observation period of safety run-in for reasons other than DLT, then a patient will need to be added to the safety run-in.

5.0 STUDY PROCEDURES AND SCHEDULE OF EVENTS**5.1 COMBINATION TREATMENT GUADECITABINE + PEMBROLIZUMAB**

Time Period	Screening		On Treatment ¹⁵			Off Treatment	
	≤28 days prior to registration	≤14 days prior to registration	Cycle 1 ¹⁴	Cycle 2	Subsequent cycles	≥ 6 months of treatment ¹⁷	30 days post last dose ¹²
Required Assessments							
Informed Consent	X						
Medical history ¹	X						
Physical exam ²		X	D1 ²	D1 ²	D1 ²		X
CBC ³		X	D1 ³	D1 ³	D		X
CMP ³		X	D1 ³	D1 ³	D		X
CA 125 ³	X		D1 ³	D1 ³	D		X
Mg, Phos, LDH		X					
PT/INR & aPTT		X					
Thyroid Function and Uric acid ¹¹		X			D1 ¹¹		
Pregnancy test	X ⁸		D1 ⁸	D1 ⁸	D1 ⁸		
Adverse events ¹⁶		X	D1	D1	D1		X
Con Meds ¹⁶		X	D1	D1	D1		X
CXR or CT of chest ⁴	X				X		X ¹³
CT or MRI of abdomen & pelvis ⁴	X				X		X ¹³
Pembrolizumab ¹⁵			D5	D5	D5		
Guadecitabine ¹⁵			D1-4	D1-4	D1-4		
Archival tumor tissue ⁵			X				
Blood for DNA analysis ⁶			C1D1	C2D8		X ¹⁷	
Blood for cytokine response ⁷			C1D1	C2D1	C3D1	X ¹⁷	X
Blood for PBMC analysis ⁹			X	X		X ¹⁷	X
Tumor biopsy ¹⁰			X	X		X ¹⁷	
Survival status							X
Subsequent therapy							X

1. Includes diagnosis and staging [pathology report and Tumor Node Metastasis (TNM) staging should be collected].

2. Physical exam includes vital signs [blood pressure, weight, height (screening only)] and ECOG performance status. Physical exam will be conducted on Day 1 (+/-4 days) of each cycle and at the safety follow-up visit, which occurs 30 days post last dose.

3. Labs to be done within ≤4 days of D1. Cycle 1 Day 1 CBC and CMP do not need to be repeated if screening labs

NU Study Number: NU 16G03

Merck Study Number: 3475-244

were done ≤ 4 days prior to starting treatment. CA-125 is to be drawn at screening and Day 1 of each cycle. Exceptions would be if CA-125 was drawn within 14 days from the screening visit or within 14 days of visits where doses have been delayed. In these cases, CA-125 will not need to be re-drawn. CBC = Complete Blood Cell Count with diff. CMP = Na, K, Cl, creatinine, BUN; liver function tests (LFTs) to include AST, ALT, total bilirubin, alkaline phosphatase.

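### In the run-in, the 7-day guadecitabine stopping rule pre-empts the delay-based DLT, so a patient stopped for guadecitabine toxicity that meets no other DLT row can be replaced instead of counted

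*Combined protocol and SAP*

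**What the plan says.** Section 4.3 treats six run-in patients and lets accrual continue if 0 or 1 has a DLT; two or more suspend the study. Section 10.4.1 repeats the rule. Besides the severity-based rows, the DLT table has a delay row: toxicity at least possibly related to study drug that "results in a >14 day delay in cycle 2 Day 1 dosing will also be considered a DLT".

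Section 4.4.1 handles drug-related toxicity that has not recovered when the next cycle is due. It permits a one-week delay and then states: "If toxicity is still not resolved after a delay of 1 week, guadecitabine will be discontinued". The same section adds: "If a patient cannot complete at least 2 cycles of guadecitabine and pembrolizumab combination, then she would be discontinued from the study".

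On replacement, Section 4.3 says of a run-in patient who goes off study "before completing the DLT observation period of safety run-in for reasons other than DLT, then that subject should be replaced". Section 4.11 says that if she goes off treatment early "for reasons other than DLT, then a patient will need to be added to the safety run-in".

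Section 4.8 has a third limit: "Delay of more than 28 days due to treatment related toxicity" leads to discontinuation of study drugs. Sections 4.4.2 and 4.10 also use 28 days.

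**The concern.** Three delay limits (7, 14 and 28 days) apply to overlapping situations, and the shortest acts before the DLT criterion can be met. A run-in patient due for cycle 2 has completed only one combination cycle. If toxicity attributed to guadecitabine keeps her from starting within seven days, she is off guadecitabine and then off study. She has not had a delay of more than 14 days, and no text says that leaving for related toxicity is a DLT. Unless another row applies, she has left for a non-DLT reason and may be replaced.

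The toxicities exposed to this gap are relevant here. Grade 3 neutropenia of any duration, Grade 4 neutropenia lasting under 7 days, Grade 3 thrombocytopenia without bleeding, and persistent Grade 2 toxicity meet no severity-based row. Section 1.3.2 names myelosuppression as a main nonclinical finding. Section 1.3.4 notes that the cycle is shortened from 28 to 21 days, and the DLT table bars growth factor. For slow recovery of counts, the delay row is the one that should register the problem.

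At stake is the formal go/no-go count for a combination that Section 4.3 describes as having no clinical experience.

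**Working it through.** **Timeline.** The inputs are the 21-day cycle (Section 4.1), the delay limits (4.3, 4.4.1) and the minimum observation period of 2 weeks after cycle 1 (4.3).

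- Cycle 2 Day 1 is due on 21 + 1 = day 22.
- The 7-day limit falls on 22 + 7 = day 29. If toxicity is unresolved, guadecitabine stops and the patient leaves the study.
- Minimum DLT observation ends on 21 + 14 = day 35.
- A 14-day delay falls on 22 + 14 = day 36, so a delay of more than 14 days first exists on day 37.

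She therefore leaves 35 − 29 = 6 days before minimum observation ends, and 37 − 29 = 8 days before the delay row could apply. Because she leaves inside the observation period, the replacement clauses apply to her.

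**Effect on the gate.** The documents state no operating characteristic for the run-in, so there is no figure to reproduce. The chance of proceeding is

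P(go) = P(X ≤ 1 | 6, p) = (1 − p)^6 + 6p(1 − p)^5.

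Let d be the rate of DLTs under the other rows, and u the rate of patients stopped only by the 7-day rule. Both are assumptions. The rate entering the rule is:

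- replaced: d/(1 − u)
- kept among the six but not called a DLT: d
- counted as a DLT: d + u

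For d = 0.10 and u = 0.10:

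- replaced: p = 0.10/0.90 = 0.111; P(go) = 0.863
- kept, not counted: p = 0.10; P(go) = 0.886
- counted: p = 0.20; P(go) = 0.262 + 0.393 = 0.655

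| d | u | P(go), replaced | P(go), kept but not counted | P(go), counted as DLT |
|---|---|---|---|---|
| 0.10 | 0.05 | 0.875 | 0.886 | 0.776 |
| 0.10 | 0.10 | 0.863 | 0.886 | 0.655 |
| 0.10 | 0.20 | 0.833 | 0.886 | 0.420 |
| 0.20 | 0.05 | 0.630 | 0.655 | 0.534 |
| 0.20 | 0.10 | 0.601 | 0.655 | 0.420 |
| 0.20 | 0.20 | 0.534 | 0.655 | 0.233 |

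The direction does not depend on the assumed values. (d + u)(1 − u) − d = u(1 − d − u), which is positive whenever u > 0 and d + u < 1, so replacement always gives a lower apparent rate than counting. The fourth column shows that keeping such a patient among the six without calling her a DLT makes the gate more permissive still.

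**The case against.** The best reply is that the gap closes on a sensible reading. Section 4.4 calls its rules suggested guidelines, Section 4.3 is specific to the run-in, and a cycle 2 never given because of toxicity could be regarded as delayed by more than 14 days. That reading is possible, but no text adopts it, and the stop in Section 4.4.1 is worded as mandatory. Section 4.11 speaks of adding a patient and does not say that the first patient's event is erased. By the text, however, she has no DLT to carry into the numerator.

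Several limits on the point do stand:

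- A reader might infer that any run-in drug toxicity can escape the count. It cannot. Grade 3 or higher non-hematological toxicity despite intervention, and the listed hematological events, are DLTs in their own right. Toxicity attributed only to pembrolizumab falls under the 28-day limit in Section 4.4.2, so the delay row can still operate there.
- A reader might infer that observation closes on day 35, before a delay of more than 14 days could be seen. Section 4.3 sets two weeks as a minimum, so day 35 is not a cut-off.
- A reader might infer that a large share of DLT-level toxicity is lost. The documents support no such share. Toxicity resolving soon enough for cycle 2 to start by day 36 would not meet the delay row even without Section 4.4.1. Counting every patient stopped at day 29 is therefore broader than the present definition, and the table shows the effect of that broader count.
- A reader might infer that the toxicity is hidden from oversight. Section 10.4.1 has all toxicities tabulated and toxicity counts and rates reviewed by the DMC, and Section 4.4 makes every dosed patient evaluable for toxicity. What is affected is the formal count.
- Rewording cannot change a run-in decision already taken. The Amendment 9 entry reports 5 patients who never started treatment and 7 who had only one cycle, 12 in all. Accrual was to pause after the first six, so the run-in appears to be over. The entry does not say why the seven stopped or whether any was a run-in patient, so it is not evidence that the gate passed wrongly.

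**Conclusion.** The point holds within this scope. For toxicity attributed to guadecitabine, alone or with pembrolizumab, that meets no other DLT row, Sections 4.3, 4.4.1 and 4.11 read literally make the delay DLT unreachable and allow the patient to be replaced. This is a conflict between rules, and its bias runs toward proceeding. Its size cannot be estimated from the documents. At the assumed d = u = 0.10 the difference in P(go) is 0.863 − 0.655 = 0.208. Across the values tabulated it runs from 0.630 − 0.534 = 0.096 to 0.833 − 0.420 = 0.413. The documents do not show that any run-in patient was in fact handled this way.

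**What to change.** Reconcile the 7-, 14- and 28-day limits in Sections 4.3, 4.4.1, 4.4.2, 4.8 and 4.10. Which limit is right is for the sponsor to decide.

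For the run-in count in Sections 4.3, 4.11 and 10.4.1, state that a patient who cannot start cycle 2, or is discontinued, because of at least possibly related toxicity is not replaced and counts as a DLT, in the numerator as well as the denominator. Limit replacement to departures unrelated to study-drug toxicity. Retaining her without classifying her would not repair the rule, as the working shows.

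As the run-in appears complete, also report whether any run-in patient was replaced after related toxicity, and give the DLT count with such patients included.

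The cost is protocol wording and a short look back at the run-in records. The run-in result may look slightly less favourable.

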4.4 Toxicity Management & Dose Delays/Modifications

Any patient who receives at least one dose of study therapy will be evaluable for toxicity endpoints. Each patient will be assessed for the development of toxicity according to the timeframe referenced in the Schedule of Events table. Toxicity will be assessed according to CTCAE v4.03.

This section provides suggested guidelines for the management of various study drug-related toxicities in subjects receiving guadecitabine and pembrolizumab. *(Note: Drug-related toxicity will be defined as any event, which is considered possibly, probably, or definitely related to the drug. It does not include toxicities clearly not related to the drug such as disease progression, environmental, unrelated trauma, etc.)*

The treating investigator should assess to the best of his/her ability whether an adverse event is possibly related to study treatment, and if so, attribute it to guadecitabine only, pembrolizumab only, or both guadecitabine and pembrolizumab, and treat the subject accordingly by only reducing the study drug that has most likely contributed to the individual toxicity necessitating dose reduction. Preferably, only one study drug should be reduced at any one time.

4.4.1 Dose modifications for Guadecitabine

Guadecitabine-related AEs will be managed with dose reductions and/or skipped doses. Guadecitabine dosing should be held for \geq grade 3 neutropenia, \geq grade 3 thrombocytopenia or other \geq grade 3 guadecitabine-related non-hematologic toxicities until toxicity has resolved to \leq Grade 1 or baseline levels (NOTE: pembrolizumab dosing may continue for that cycle if the toxicity is documented to be related only to guadecitabine). Treatment with guadecitabine may then be resumed for the next cycle at dose level -1 (which is 24 mg/m² – see Section 4.2). Missed doses will not be made up. Exceptions for the dose reductions would include neutropenia and anemia which could be managed by growth factors and transfusion, and in that case dosing may be resumed at the same dose level. After completion of the safety run in, starting on Day 5 of each cycle, growth factor support filgrastim or peg filgrastim can be administered 24 hours after completion of guadecitabine administration, at the discretion of the treating physician.

NU Study Number: NU 16G03
Merck Study Number: 3475-244

If the subject still has drug-related clinically significant toxicity that has not resolved to ≤ Grade 1 or baseline by the time of the next cycle, dosing for that cycle may be delayed 1 week (7 days). Dosing may restart at dose level -1 (24 mg/m²) once the toxicity has resolved to ≤ Grade 1 or baseline. If toxicity is still not resolved after a delay of 1 week, guadecitabine will be discontinued. If the patient has already completed 2 cycles of combination therapy at this point, the patient may be a candidate for continuing on single-agent pembrolizumab (see below).

If grade 3-4 toxicity reoccurs after treatment has been restarted at dose level -1 (24mg/m²), and the patient has received at least 2 cycles of guadecitabine priming, then guadecitabine can be discontinued permanently and pembrolizumab can be continued as a single agent on the same dose schedule.

Rationale for continuing single-agent pembrolizumab:

There is presumptive scientific rationale that treatment with a hypomethylating agent will cause re-expression of tumor antigens within the first 2 cycles, and thus epigenetic priming, which enhances the effects of immunotherapy. Therefore, it is reasonable to continue treatment with single agent pembrolizumab after epigenetic priming has been induced. If a patient cannot complete at least 2 cycles of guadecitabine and pembrolizumab combination, then she would be discontinued from the study.

Please note: Guadecitabine priming can be discontinued and the patient can continue on pembrolizumab monotherapy after 6 months (8 cycles), at the discretion of the treating physician, if the patient has stable disease or response. For patients who discontinued guadecitabine for reasons other than toxicity (i.e. disease stability of response > 6 months) and progress on pembrolizumab alone, a re-trial of guadecitabine in combination with pembrolizumab is possible, at the discretion of the treating physician, if the patient is clinically stable.

